8.2. Statistical and analytical methods

The primary endpoint will be the AUC of the receiver operator characteristic (ROC) curves for the biomarkers predicting AC20 response at week 14. We assume that 60% of the patients will respond to abatacept therapy based on the data from the AMPLEx trial (31). Thus, a total sample size of 25 patients will yield approximately 15 responders and 10 non-responders. With this sample, the expected margin of error for 95% confidence intervals for the AUC will be 19% or 22% if the AUC is 0.8, or 0.7, respectively (32). This is a pilot study and the results from this study would be assessed in other cohorts with bigger subject numbers.

For each candidate biomarker, we will compute receiver operating characteristic (ROC) curves related to response rate to abatacept therapy. We will consider a patient to have responded positively to abatacept if they achieve ACR 20 response at week 14.

The area under the ROC curve (AUC) will be the primary measure of the predictive value of the biomarker. Estimates of the AUC's and 95% confidence intervals will be computed for each biomarker. We will also evaluate the predictive value of combinations of any or all baseline biomarker information used in linear risk scores derived using logistic regression models (outcome = response to abatacept therapy). We will evaluate each possible risk-score combination of biomarkers as a predictor by estimating the prediction error using leave-one-out cross-validation (at the 80% specificity cutoff). Similar analyses will be run evaluating the predictive power of the secondary-objective baseline patient characteristics

9. Reference List

2. Dennis G Jr, Holweg CT, Kummerfeld SK, Choy DF, Setiadi AF, Hackney JA, Haverty PM, Gilbert H, Lin WY, Diehl L, Fischer S, Song A, Musselman D, Klearman M, Gabay C, Kavanaugh A, Endres J, Fox DA, Martin F, Townsend MJ. Synovial phenotypes in rheumatoid arthritis correlate with response to biologic therapeutics. *Arthritis Res Ther.* 2014;16(2):R90

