follicular helper cells (Tfh) which primarily function in lymph nodes. One of the primary functions of Tfh and Tph cells is to stimulate differentiation of B cells into antibody-secreting plasma cells. Both Tfh and Tph pathways are associated with IL-21 and CXCL13, cytokines known to support GC formation and plasma cell differentiation. Serum CXCL13 levels are higher in seropositive RA (27) and may predict the therapeutic response in RA (28).

It has been reported that abatacept is more effective in anti-CCP-positive RA patients (1) and suppresses Tfh cell maturation and proliferation in murine models of RA (12). Abatacept treatment in patients with primary Sjogren's syndrome was recently reported to reduce circulating Tfh cells and lower the expression of the activation marker ICOS on T cells (29). Regarding B cell activation, abatacept has been shown to reduce serum ACPA and RF and lower the frequencies of post-switched memory B cells in RA (30). These results suggest that, inhibition of activated Tfh (and Tph) cells, leading to attenuated T cell-dependent B cell activation may underlie the efficacy of abatacept.

The intent of this study is to demonstrate whether baseline levels of the above biomarkers are helpful in predicting the response to abatacept in RA patients who have an inadequate response to methotrexate and other conventional disease modifying anti-rheumatic drugs (cDMARDs). Further evaluation of the effects of abatacept on the phenotypic distribution of circulating T cell and B cell subsets will provide additional information regarding action mechanisms of abatacept.

2. Objectives

The primary objective of this study is

- To evaluate if baseline levels of T cell-associated biomarkers and other biomarkers predict efficacy of abatacept during 24 weeks of treatment in patients with moderate to severe active RA who have had an inadequate response to cDMARDs

The secondary objectives of this study are

- To evaluate change in phenotypic distribution of circulating T cell and B cell subsets, T cell-associated biomarkers and other biomarkers with subcutaneous abatacept in moderate to severe RA patients

3. Ethical Considerations

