- Blood samples for laboratory tests: Complete Blood Count (CBC), Comprehensive Metabolic Panel (CMP), Erythrocyte Sedimentation Rate (ESR), C Reactive Protein (CRP), IgG, IgM and IgA rheumatoid factor, IgG and IgA anti-CCP, Immunoglobulins G, M, A
- Biomarker blood draw (serum, PBMC)
- Joint exam
- Complete physical exam
- Vitals signs: blood pressure, pulse, temperature, weight, height
- Physician's global assessment
- Physician safety assessment
- Ultrasound exam
- Adverse event review
- Medication review
- For women of childbearing potential, a urine pregnancy test should be completed prior to dispensing study medication
- Study drug (abatacept) dispensation and in clinic injection

Treatment visit (Weeks 6, 14, 24)

Patients must return to the clinic for assessments at weeks 6, 14 and 24. The following procedures and assessments are to be completed during the treatment visits.

- Patient self-assessment measures: MDHAQ, PGA, FACIT-F, SF-12
- Blood samples for laboratory tests: Complete Blood Count (CBC), Comprehensive Metabolic Panel (CMP), Erythrocyte Sedimentation Rate (ESR), C Reactive Protein (CRP), IgG, IgM and IgA rheumatoid factor, IgG and IgA anti-CCP, Immunoglobulins G, M, A
- Biomarker blood draw (serum, PBMC)
- Joint exam

- Symptom targeted physical exam
- Vital signs including blood pressure, pulse, temperature, and weight
- Physician's global assessment
- Physician safety assessment
- Ultrasound exam (weeks 14 and 24)
- Adverse event review
- Medication review
- Study drug (abatacept) dispensation and in clinic injection

Follow-up telephone contact (4 & 15 weeks after the final treatment visit)

Patients receive a follow-up phone call from study personnel 4 weeks and 15 weeks after the week 24 visit. Patients who discontinue from the study early will have telephone visits at 4 weeks and 15 weeks after their end of treatment visit, if continued follow up is acceptable. The following procedures and assessments are to be completed at the follow-up telephone contact.

- Follow-up on transition to standard of care (PT Week 4 only)
- Follow-up on any adverse events

7. Safety and Reporting

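### Multi-marker logistic scores are planned without a penalty or size limit in about 15 v 10 patients, so the largest will usually separate the groups completely and have no finite coefficients; a penalised fit is a cheap improvement.

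*Combined protocol and SAP*

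**What the plan says.** Section 8.2, repeated in the statistical paragraph of the synopsis, adds a multi-marker analysis to the single-marker ROC curves. It will assess "combinations of any or all baseline biomarker information used in linear risk scores derived using logistic regression models". The search is exhaustive: "We will evaluate each possible risk-score combination of biomarkers as a predictor". Scores are judged by "estimating the prediction error using leave-one-out cross-validation (at the 80% specificity cutoff").

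The data are few: "a total sample size of 25 patients will yield approximately 15 responders and 10 non-responders". Section 8.2 sets no upper limit on markers per score, no penalised or bias-reduced fit, and no rule for separation or non-convergence.

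No marker count is given. Section 1 says the study asks whether "baseline levels of the above biomarkers are helpful in predicting the response to abatacept", after naming 14 soluble markers. The baseline laboratory list in section 6 adds "IgG, IgM and IgA rheumatoid factor, IgG and IgA anti-CCP".

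Section 8.2 makes the AUC of each single marker the primary measure and calls the study a pilot, to be followed up in larger cohorts.

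**The concern.** A logistic model with many predictors and few patients can often find a linear rule that puts every responder on one side and every non-responder on the other. The likelihood then has no maximum. Coefficients grow without bound, and the reported values depend on where the software stops.

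The plan includes the score that uses all markers, so this case is planned and not hypothetical. Separation also becomes more likely as more markers carry real information. At stake are whether the larger scores can be written down and tested in the later cohorts, and how well they predict.

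**Working it through.** **Inputs.** N = 25, split 15/10 (section 8.2). Assumed: maximum-likelihood fitting, since the text says only logistic regression. Assumed marker count p = 14, counted from section 1: sCD27, sCD28, sCTLA4, sCD40L, sCD137, sICOS; sCD14, sCD163, calprotectin, MPO-DNA, sCD25, sCD23; CXCL10, CXCL13. Three RF and two anti-CCP isotypes make 19; ESR and CRP make 21.

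**1. The plan's own figure.** It states a "margin of error for 95% confidence intervals for the AUC will be 19% or 22% if the AUC is 0.8, or 0.7". The Hanley-McNeil formula is SE² = [A(1−A) + (a−1)(Q₁−A²) + (b−1)(Q₂−A²)]/(ab), with Q₁ = A/(2−A) and Q₂ = 2A²/(1+A). Take a = 10 and b = 15.
- A = 0.8: (0.16 + 9×0.0267 + 14×0.0711)/150 = 0.00930; SE = 0.0965; ×1.96 = 18.9%.
- A = 0.7: (0.21 + 9×0.0485 + 14×0.0865)/150 = 0.01238; SE = 0.1113; ×1.96 = 21.8%.

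The stated 19% and 22% are reproduced. They concern one AUC at a time and say nothing about multi-marker fits.

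**2. Probability of complete separation, uninformative markers.** Cover's formula for a linear score with intercept, equal class odds: P = 2^−(n−1) × Σ C(n−1, k), k = 0 to p. For n = 25, p = 14: 1 − 2,579,130/16,777,216 = 0.846. For a leave-one-out set of n = 24 it is 0.895.

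| Markers in score | Uninformative (Cover, n = 25) | One marker with AUC 0.8 | Three markers with AUC 0.7 |
|---|---|---|---|
| 3 | 0.01% | 0.8% | 3.2% |
| 6 | 1.1% | 13% | 19% |
| 8 | 7.6% | 35% | 42% |
| 10 | 27% | 66% | 66% |
| 12 | 58% | 83% | 91% |
| 14 | 85% | 97% | 97% |

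The last two columns are linear-programming checks on a fixed 15/10 split, 500 data sets per cell, independent normal markers. The same check with 14 uninformative markers gave 85%, in line with Cover. With pairwise correlation 0.3 and three informative markers, runs gave about 98% at 14 markers, 86% to 90% at 12 and 58% to 70% at 10.

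**3. Share of the planned scores.** There are 2^14 − 1 = 16,383 combinations. Weighting each size by its Cover probability, Σ C(14,k)P(k) = 1,174, or 7.2%. Only 91×0.581 + 14×0.729 + 1×0.846 ≈ 64 of these have 12 or more markers. Most come from mid-sized scores, which separate less often but are far more numerous. With three informative markers, simulation gives about 23%. With 19 markers the shares are about 27% and 46%; with 21 uninformative markers, 38%.

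**4. The 80% specificity cutoff.** Under separation the training data already show full sensitivity at full specificity. A cutoff at 80% specificity misclassifies 2 of 10 training non-responders for no gain in sensitivity, and any threshold in the gap fits equally well.

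**5. What leave-one-out reports.** With uninformative markers, going from 1 to 18 per score, the in-sample AUC rose from 0.59 to 1.00 while leave-one-out error went only from 0.57 to 0.46. For 14 markers, error was 0.39 with three informative and 0.48 with none. Changing the number of fitting iterations moved about 1 of 25 held-out classifications (1.5 when stopping at 4 instead of 20; 4%, or 1 of 25, at 6 instead of 20).

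**6. What a penalty gains.** 14 markers, three informative: ridge lowered leave-one-out error from 0.39 to 0.34 (0.05×25 = 1.25 patients) and raised AUC in new patients from 0.64 to 0.71.

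**The case against.** The strongest reply is that the plan does not judge scores by coefficients or in-sample fit. It judges them by held-out error. When coefficients diverge, a linear rule and a cutoff on it still exist, and leave-one-out error still measures how that rule predicts an omitted patient. This stands, and step 5 bears it out. A reader might infer that the larger scores are artefacts whose cross-validated error estimates nothing. The planned validation rules that out: it still distinguishes signal from noise and does not report a perfect fit as real.

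A reader might also infer that most of the planned analysis fails. With 14 markers, 77% to 93% of combinations would not separate. The higher shares need 19 or more candidates, counting RF and anti-CCP, which section 6 lists with laboratory tests and apart from the biomarker draw.

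Two further points stand. Maximum likelihood is the natural reading of an unqualified reference to logistic regression, but it is an inference. And the single-marker AUC, the primary measure, needs no multivariable fit.

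The pilot label does not dispose of the point. Results are meant to be assessed in other cohorts, and a score without finite coefficients cannot be carried there as a fixed rule.

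**Conclusion.** The point holds as a cheap improvement to the secondary, multi-marker part of section 8.2. With about 15 v 10 patients and unpenalised fitting, scores of about 12 or more markers (about 10 or more if some are informative) will usually have no finite estimates. Counting all sizes, that affects about 7% to 23% of the 16,383 combinations of 14 markers. The consequences are coefficients that cannot be transported, a poorly defined cutoff, a small dependence on software settings, and weaker prediction than a penalised fit would give.

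This rests on maximum-likelihood fitting, a marker count of 14 that the plan does not state, simulated normal markers, and assumed effect sizes and correlation. The sensitivity to stopping point varies with the algorithm and settings compared. The ridge gains are simulation averages; one study of 25 patients could not demonstrate them.

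Optimism from choosing the best of thousands of scores by the same leave-one-out error is a separate matter, which a penalty alone does not remove.

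**What to change.** In section 8.2 and the synopsis, state that multi-marker scores are fitted by ridge (or Firth) penalised logistic regression on standardised marker values. State also that standardisation, any tuning of the penalty and the 80% specificity cutoff are re-derived inside each leave-one-out fold. Either method deals with separation; the gains in step 6 were computed for ridge only.

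A limit on score size is optional. For example, at most three of 14 markers leaves 14 + 91 + 364 = 469 scores, but larger combinations would go unexplored, and a penalised fit does not need the limit.

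The cost is a change of wording, standard software, slightly more analysis work and coefficients shrunk towards zero. No patient procedure or sample size changes.

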Assessment	
Primary endpoint
 
 Baseline levels of T cell-associated biomarkers or other biomarkers predict ACR20 response with subcutaneous abatacept at week 14 
Secondary endpoints
 
 Baseline levels of T cell-associated biomarkers or other biomarkers predict ACR20 response with subcutaneous abatacept at week 24 Baseline levels of T cell-associated biomarkers or other biomarkers predict ACR50 & 70 response, EULAR good or moderate response, low disease activity (DAS28 < 3.2 or CDAI ≤ 10) or remission (DAS28 < 2.6 or CDAI ≤ 2.8) with subcutaneous abatacept at week 14 and 24 Change in phenotypic distribution of circulating T cell and B cell subsets, T cell-associated biomarkers and other biomarkers with subcutaneous abatacept at week 14 and 24 Adverse event monitoring
Statistical analysis	The primary endpoint will be the AUC of the receiver operator characteristic (ROC) curves for the biomarkers predicting AC20 response at week 14. We assume that 60% of the

patients will respond to abatacept therapy based on the data from the AMPLE trial. Thus, a total sample size of 25 patients will yield approximately 15 responders and 10 non-responders. With this sample, the expected margin of error for 95% confidence intervals for the AUC will be 19% or 22% if the AUC is 0.8, or 0.7, respectively.

The area under the ROC curve (AUC) will be the primary measure of the predictive value of the biomarker. Estimates of the AUC's and 95% confidence intervals will be computed for each biomarker. We will also evaluate the predictive value of combinations of any or all baseline biomarker information used in linear risk scores derived using logistic regression models (outcome = response to abatacept therapy). We will evaluate each possible risk-score combination of biomarkers as a predictor by estimating the prediction error using leave-one-out cross-validation (at the 80% specificity cutoff).

Table of Contents

1. Background and rationale
2. Objectives
3. Ethical considerations
 - 3.1. Good clinical practice
 - 3.2. Institutional review board
 - 3.3. Informed consent
4. Study Design
 - 4.1. Overview of study design
 - 4.2. Eligibility
 - 4.3. Concomitant medication and treatment
 - 4.4. Premature withdrawal
5. Study Drug/Treatment
 - 5.1. Investigational Product (IP)
 - 5.2. Storage, Administration, and Destruction of Investigational Product
6. Study procedures
7. Safety and Reporting

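### Section 8.2 scores every biomarker combination with a single level of leave-one-out cross-validation, so the error of a combination picked as best would look too low

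*Combined protocol and SAP*

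**What the plan says.** Section 8.2 makes the AUC of each single biomarker the primary measure. It then adds an evaluation of "combinations of any or all baseline biomarker information used in linear risk scores derived using logistic regression models", with response to abatacept as the outcome. On how these scores are judged it says: "We will evaluate each possible risk-score combination of biomarkers as a predictor by estimating the prediction error using leave-one-out cross-validation", with the error taken at an 80% specificity cutoff. The statistical part of the synopsis repeats this.

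On size, Section 8.2 says that "a total sample size of 25 patients will yield approximately 15 responders and 10 non-responders". It also says: "This is a pilot study and the results from this study would be assessed in other cohorts with bigger subject numbers".

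Neither place gives a closed list of candidate markers, a limit on markers per score, a rule for choosing or reporting a combination, an outer validation loop, a permutation test or a hold-out set. The nearest thing to a list is in Section 1: "The intent of this study is to demonstrate whether baseline levels of the above biomarkers are helpful in predicting the response to abatacept". That refers back to the markers discussed earlier in that section.

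**The concern.** Leave-one-out error is approximately fair for one score whose markers were fixed before the data were seen. The plan produces one such error for every subset of markers, all from the same 25 patients. The lowest of many noisy estimates is biased downward, because it partly picks out the subset that chance favoured. The patient held out in each fold has also helped to decide which subset wins, so that patient is no longer independent of the reported score.

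The plan does not say that a best combination will be picked. But a search over all subsets has few other uses, and any panel carried forward to other cohorts would have to be picked from it. A panel with no predictive value could then be reported with an encouraging error and taken to the next study.

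A separate difficulty is that an ordinary logistic model with many markers can separate 25 patients perfectly. It then has no finite maximum likelihood fit.

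**Working it through.** **1. Inputs from the plan.** 25 patients, 60% response, so 15 responders and 10 non-responders; logistic scores; leave-one-out error at 80% specificity (Section 8.2).

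**2. The plan's own figure.** Section 8.2 says "the expected margin of error for 95% confidence intervals for the AUC will be 19% or 22% if the AUC is 0.8, or 0.7, respectively". By Hanley-McNeil, the standard error is √{[A(1−A) + (n₁−1)(Q₁−A²) + (n₂−1)(Q₂−A²)]/(n₁n₂)}, with Q₁ = A/(2−A) and Q₂ = 2A²/(1+A). With n₁ = 10 and n₂ = 15:

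- A = 0.8: √[(0.16 + 9×0.0267 + 14×0.0711)/150] = 0.0965; ×1.96 = 0.189.
- A = 0.7: √[(0.21 + 9×0.0485 + 14×0.0865)/150] = 0.1113; ×1.96 = 0.218.

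Both agree with the plan. They concern single markers and say nothing about the combination search.

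**3. Number of combinations (assumed range).** Section 1 discusses six soluble T cell markers: sCD27, sCD28, sCTLA4, sCD40L, sCD137 and sICOS. Adding sCD14, sCD163, calprotectin, MPO-DNA, sCD25, sCD23, CXCL10 and CXCL13 makes 14. All subsets: 2⁶−1 = 63 and 2¹⁴−1 = 16,383. For 14 markers, up to pairs is 14+91 = 105, and up to triples is 105+364 = 469.

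**4. Simulation with no information in any marker.** Independent normal markers, 15 v 10 patients. Logistic scores used a very small ridge (0.01) so that fits converge. Error is the overall misclassification rate. The cutoff is the lowest value giving at least 80% specificity among non-responders. The plan does not say where the cutoff is set, so two rules are shown: in each training fold / on the pooled held-out scores.

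| Search | Runs | Mean error over all scores | Error of the best score |
|---|---|---|---|
| 6 markers, all 63 | 400 | 0.49 / 0.57 | 0.28 / 0.38 |
| 14 markers, up to pairs (105) | 200 | 0.49 / 0.58 | 0.22 / 0.28 |
| 14 markers, up to triples (469) | 200 | 0.49 / 0.57 | 0.19 / 0.25 |
| 14 markers, all 16,383 | 25 | 0.47 / 0.55 | 0.15 / 0.20 |

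Calling everyone a responder has error 10/25 = 0.40. The best noise score beats that in 87% / 56% of runs with 6 markers, and in all 25 full-search runs with 14 markers under both rules. Separate runs of the 6-marker case gave 0.27 to 0.31 / 0.36 to 0.39 for the best score.

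**5. Where the optimism comes from.** With the fold-wise cutoff, the selected 6-marker score has error 0.49 to 0.50 on 5,000 new patients, close to the unselected average of 0.49. Leave-one-out itself is therefore sound here, and taking the minimum is what fails. Correlating the noise markers at 0.5 gives 0.29 reported v 0.50 on new patients.

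**6. With one real marker of AUC 0.8 among six (fold-wise cutoff).** The best score reports 0.18 to 0.19, against 0.32 to 0.33 on new patients.

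**7. Does nesting repair it?** Selection, fit and cutoff were repeated inside each outer training set of 24.

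- 6 noise markers (200 runs): 0.288 becomes 0.480 (fold-wise) and 0.383 becomes 0.505 (pooled); SE about 0.01.
- 14 noise markers, up to pairs (60 runs): 0.233 becomes 0.481 and 0.295 becomes 0.485; SE about 0.02.
- One real marker among six (60 runs, fold-wise): 0.184 becomes 0.298 (SE 0.014), against 0.322 on new patients.

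**8. Perfect separation of the full model on noise.** Cover's theorem gives P(Bin(24, 0.5) ≤ p): 0.01 for 6 markers, 0.27 for 10, 0.58 for 12 and 0.85 for 14. Linear programming on 600 simulated 15 v 10 data sets for each p gave 0.01, 0.26, 0.60 and 0.84.

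**The case against.** - **No selection is stated.** The plan says only that combinations will be evaluated. If every error were reported and none chosen, this bias would not arise. That stands, and the conclusion is conditional on a choice being made.
- **It is an additional analysis in a pilot.** The single-marker AUCs are primary and untouched, and later cohorts could expose a useless panel. This limits the consequence. It does not correct the error this study would report or the choice of panel to carry forward.
- **The definitions are assumed.** The plan defines neither prediction error nor the group on which specificity is measured, and its AUC margins are reproduced only with the 10 non-responders as the abnormal group. Defining specificity on responders instead (6 markers, 150 runs) gave best v average errors of 0.27 v 0.44 (fold-wise) and 0.32 v 0.45 (pooled). The best score beat 0.40 in 97% and 78% of runs. The gap is smaller but remains. Reading prediction error as missed responders only was not simulated.
- **A textbook benchmark is not like with like.** A binormal AUC of 0.80 at exactly 80% specificity has error 0.6×(1−0.636) + 0.4×0.2 = 0.30. The fold-wise rule does not attain 80% specificity in held-out patients, so fold-wise minima should not be set against 0.30. The fair fold-wise comparison is 0.28 reported for noise against 0.32 to 0.33 on new patients for a selected score when one marker is real.
- **The short-list, pooled-cutoff case is mild.** 0.38 against 0.40 is less than one patient in 25. That stands.
- **The largest figures are the least secure.** The full 14-marker search rests on 25 runs. The conclusion does not need it.

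**Conclusion.** The concern holds. If a combination is picked from this search and reported with its leave-one-out error, that error will be too low. The direction was the same in every setting examined: independent or correlated noise, one real marker, either cutoff rule, and either definition of specificity.

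The size is illustrative, because it rests on an assumed 6 to 14 normally distributed markers and on error meaning overall misclassification. For noise, the drop from average to best score is about 0.2 with 6 markers (0.49 to 0.28, or 0.57 to 0.38). It is about 0.3 with 14 markers (0.49 to 0.22, or 0.58 to 0.28, up to pairs; more with larger subsets). The problem is moderate for a short list and strong for a long one. Perfect separation is a further obstacle with long lists only.

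This should be fixed before analysis, although it does not touch the primary measure.

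**What to change.** After the leave-one-out sentence in Section 8.2 and in the synopsis, add:

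> If any combination is selected from this search, marker selection, coefficient fitting and the 80% specificity cutoff will be repeated inside every leave-one-out training set, and the outer-loop error will be reported for the selected score. A permutation p-value will be given for the whole search.

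Also:

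- Name the candidate markers, and preferably cap the number per score. Pre-specifying a few combinations is an acceptable alternative to the search.
- Use a penalised logistic fit (ridge, lasso or Firth).
- Define prediction error, the group on which specificity is measured, and whether the cutoff is set in each fold or on pooled held-out scores.
- Optionally report a cross-validated AUC alongside.

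At the least, any selected panel's error should be labelled exploratory and unadjusted for selection. That prevents overclaiming but does not supply a usable error.

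**Cost.** Wording and computing time, with no new data. Nesting takes 63×25×24 = 37,800 fits for 6 markers (under a second on one core) and 105×25×24 = 63,000 for 14 markers up to pairs. The uncapped 14-marker search needs 16,383×25×24, about 9.8 million fits, before any permutations, which is a practical reason for a cap. Reported accuracy will look less favourable. It will also be imprecise: the SE of 0.020 over 60 nested noise runs implies a standard deviation of 0.020×√60, about 0.15, for a single study of 25 patients.

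### Risk scores are judged only by leave-one-out error at an 80% specificity cutoff, which is not on the scale of the primary AUC and, read as total misclassification, moves with the response rate

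*Combined protocol and SAP*

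**What the plan says.** For single biomarkers, section 8.2 states: "The area under the ROC curve (AUC) will be the primary measure of the predictive value of the biomarker". It adds: "Estimates of the AUC's and 95% confidence intervals will be computed for each biomarker". The plan also combines baseline markers into "linear risk scores derived using logistic regression models (outcome = response to abatacept therapy"), and assesses each possible combination by "estimating the prediction error using leave-one-out cross-validation (at the 80% specificity cutoff"). The statistical analysis row of the synopsis repeats this.

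The planning inputs are in the same section. On the response rate: "We assume that 60% of the patients will respond to abatacept therapy". On the split: "a total sample size of 25 patients will yield approximately 15 responders and 10 non-responders". The expected 95% margin of error for the AUC "will be 19% or 22% if the AUC is 0.8, or 0.7, respectively".

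Neither place defines prediction error, says how the cutoff is obtained from the training data, gives a reference error, asks for sensitivity and specificity separately, or plans a cross-validated AUC for the scores. Section 8.2 describes the study as a pilot whose results would be taken to larger cohorts.

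**The concern.** A natural question for this study is whether a combination of markers predicts response better than the best single marker. The plan states an AUC for one side of that comparison and an error rate at one operating point for the other.

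In its ordinary sense, prediction error at a cutoff is the share of patients misclassified. That share weights missed responders by the response rate and false positives by its complement. With specificity held at 80%, the false-positive part is fixed at 0.4 × 0.2 = 8 points when 60% respond, so the total is driven by missed responders. Its reference values are not obvious: a worthless score does not err 50% of the time, and the rule that ignores the markers errs 40%. A reader given an error near 40% with no benchmark could discard a score that has real discrimination, or keep one that has little.

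Because the weights are the response rate, the same score would also show a different error in a later cohort with a different response rate.

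**Working it through.** **Inputs.** All from section 8.2: 60% responders; 15 responders and 10 non-responders; planning AUCs 0.70 and 0.80; specificity 80%; response as the modelled outcome. **Assumptions added here:** prediction error means total misclassification; specificity is the share of non-responders correctly classified; equal-variance binormal ROC curve.

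**1. The plan's own figure.** Hanley-McNeil standard error, with A the AUC, Q1 = A/(2 − A), Q2 = 2A²/(1 + A):

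SE² = [A(1 − A) + (n₁ − 1)(Q1 − A²) + (n₂ − 1)(Q2 − A²)] / (n₁n₂)

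With n₁ = 10 and n₂ = 15, 1.96 × SE is 18.9% at A = 0.80 and 21.8% at A = 0.70. These match the stated 19% and 22%. With n₁ = 15 and n₂ = 10 the values are 17.3% and 20.7%. The planning AUCs are therefore used below as the plan gives them.

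**2. Expected error at true 80% specificity.** d = √2 × Φ⁻¹(AUC); sensitivity = Φ(d − 0.8416); error = 0.6 × (1 − sensitivity) + 0.4 × 0.2.

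| True AUC | d | Sensitivity | Error |
|---|---|---|---|
| 0.50 | 0 | 20.0% | 0.6 × 0.800 + 0.08 = 56.0% |
| 0.70 | 0.742 | 46.0% | 0.6 × 0.540 + 0.08 = 40.4% |
| 0.80 | 1.190 | 63.6% | 0.6 × 0.364 + 0.08 = 29.8% |

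Calling everyone a responder errs 1 − 0.6 = 40%. Break-even needs sensitivity 1 − 0.32/0.6 = 46.7%, which corresponds to an AUC of 0.704. The lowest error over all cutoffs at AUC 0.70 is 33.6%, so the fixed cutoff, and not only the score, produces the 40.4%.

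**3. Dependence on the response rate.** Same score (AUC 0.70, sensitivity 46.0%, specificity 80%):
- 55% responders: 0.55 × 0.540 + 0.45 × 0.2 = 38.7%, against 45% for calling everyone a responder.
- 65% responders: 0.65 × 0.540 + 0.35 × 0.2 = 42.1%, against 35%.

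The comparison with the benchmark reverses although discrimination is unchanged.

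**4. Dependence on ROC shape and coding.** At AUC 0.70 and 60% responders, unequal-variance binormal curves (SD ratio 0.5 to 2) give errors of 34% to 50%, and a power-law curve gives 38%. If non-response were the positive class, the error would be 0.4 × 0.540 + 0.6 × 0.2 = 33.6%.

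**5. Finite sample.** I simulated leave-one-out with 15 v 10, one marker of fixed direction, true AUC 0.70, and the cutoff re-set in each fold. Mean error was about 36% when the cutoff was the order statistic giving at least 80% specificity in the training data, and about 40% to 42% under other quantile conventions. The SD between trials was about 12 points. The estimate was 40% or worse in about 43% to 62% of trials, again by convention alone.

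**6. Basis of the cutoff.** It is set by about 10 non-responders. The exact 95% confidence interval for 8 of 10 is 44% to 97%.

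**7. The alternative.** There are 15 × 10 = 150 responder/non-responder pairs. Simulated leave-pair-out AUC for a one-marker score averaged 0.51, 0.69 and 0.79 at true AUC 0.50, 0.70 and 0.80, with an SD of about 0.1 to 0.2.

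**The case against.** The strongest reply has four parts.

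*Prediction error is undefined.* The parenthesis about the cutoff could mean that the missed-responder rate at 80% specificity is reported. That stands as a reading. Total misclassification is the usual sense, but every error figure above is conditional on it. If something else is meant, the text still needs to say so.

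*The scales can be bridged.* A ROC curve is planned for every biomarker, so its sensitivity at 80% specificity can be read off. Combinations of any or all baseline information can include one-marker scores, which would pass through the same leave-one-out procedure. Nothing forbids an AUC for the scores. This stands: a reader might infer that the plan is unable to compare combinations with single markers, and the documents do not support that. What is missing is a stated common measure, and an error-to-error comparison would keep the cutoff and response-rate problems.

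*Total error ranks scores correctly.* At a truly fixed specificity and response rate, error = 0.08 + 0.6 × (1 − sensitivity), so it orders scores as sensitivity does. This is correct within one population. It does not carry over to cohorts with other response rates, and specificity is not truly fixed when about 10 patients set the cutoff.

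*The stakes are modest.* The scores are an additional analysis in a pilot, and the proposed AUC is no more precise than the error rate. Both stand. The gain is a common scale that does not depend on the response rate, not precision.

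**Conclusion.** The concern holds in a limited form. Single markers and risk scores are given different measures with no common one stated. If prediction error means total misclassification, the measure for the scores depends on the response rate and on an unstated cutoff rule, and it comes without a benchmark.

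As to size, a score at the plan's lower planning AUC of 0.70 has an expected error of 40.4%, or about 36% to 42% in simulated leave-one-out, close to the 40% from calling everyone a responder. This rests on an equal-variance binormal curve, exactly 60% responders, response as the positive class, and total error.

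A reader might infer that an AUC-0.70 score always errs as often as the call-everyone rule, or would look useless. The documents do not support that. The ROC shape is not stated, the 60% is itself an assumption, plausible alternatives run from 34% to 50%, and a change of five points in the response rate tips the comparison either way. The mismatch of scales and the dependence on the response rate do not rely on the ROC shape. This is a worthwhile, low-cost improvement to an additional analysis; it does not affect the primary single-marker AUC.

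**What to change.** In section 8.2 and the synopsis:

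- Add a leave-pair-out cross-validated AUC for each risk score (150 refits per score at 15 v 10) as the measure for comparing scores with single markers, and run one-marker scores through the same procedure.
- Do not obtain this AUC by pooling leave-one-out scores into one ROC curve. For a one-marker logistic score, simulation of that shortcut gave 0.29, 0.58 and 0.73 at true AUC 0.50, 0.70 and 0.80.
- Keep the 80% specificity point as a descriptive result. Report cross-validated sensitivity and specificity separately with exact confidence intervals, with the cutoff re-set within each fold by a stated rule, against the no-value sensitivity of 20%.
- Define prediction error. If total error is also shown, give the call-everyone benchmark beside it (40% at the planned response rate).

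The cost is SAP wording and extra refits, with no new patients, samples or visits. The drawback is that the cross-validated AUC will be imprecise at 25 patients (simulated SD about 0.1 to 0.2) and should be reported as such. The simulations here used one marker; multi-marker scores were not checked.
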